### 13.2 When to Report an Event in an Expedited Manner

- Some adverse events require notification **within 24 hours** (refer to Table A) via the web at <http://ctep.cancer.gov> (email the ADVL1414 COG Study Assigned Research Coordinator within 24 hours of becoming aware of the event if the CTEP-AERS 24-Hour Notification web-based application is unavailable) and by telephone call to the Study Chair. Once internet connectivity is restored, a 24-hour notification phoned in must be entered electronically into CTEP-AERS by the original submitter at the site.
- When the adverse event requires expedited reporting, submit the report **within 5 or 7 calendar days** of learning of the event (refer to [Table A](#)).
- Expedited AE reporting for this study must only use CTEP-AERS (Adverse Event Expedited Reporting System), accessed via the CTEP home page <https://eapps-ctep.nci.nih.gov/ctepaers>.

### 13.3 Expedited Reporting Methods

#### 13.3.1 CTEP-AERS Reporting

To report adverse events in an expedited fashion use the NCI's Adverse Event Expedited Reporting System (CTEP-AERS) that can be found at <http://ctep.cancer.gov>.

An CTEP-AERS report must be submitted electronically via the CTEP-AERS

THIS PROTOCOL IS FOR RESEARCH PURPOSES ONLY, SEE PAGE 1 FOR USAGE POLICY

Web-based application located at <https://eapps-ctep.nci.nih.gov/ctepaers>. If prompted to enter a sponsor email address, please type in: [contact].

Email supporting documentation to the ADVL1414 COG Study Assigned Research Coordinator. **ALWAYS include the ticket number on all emailed documents.**

#### 13.4 Definition of Onset and Resolution of Adverse Events

**Note:** These guidelines below are for reporting adverse events on the COG data submission forms and do not alter the guidelines for CTEP-AERS reporting.

- 13.4.1 If an adverse event occurs more than once in a course (cycle) of therapy only the most severe grade of the event should be reported.
- 13.4.2 If an adverse event progresses through several grades during one course of therapy, only the most severe grade should be reported.
- 13.4.3 The duration of the AE is defined as the duration of the highest (most severe) grade of the Adverse Effects.
- 13.4.4 The resolution date of the AE is defined as the date at which the AE returns to baseline or less than Grade 1, whichever level is higher (note that the resolution date may therefore be different from the date at which the grade of the AE decreased from its highest grade). If the AE does not return to baseline the resolution date should be recorded as "ongoing."
- 13.4.5 An adverse event that persists from one course to another should only be reported once unless the grade becomes more severe in a subsequent course. An adverse event which resolves and then recurs during a different course, must be reported each course it recurs.

#### 13.5 Other Recipients of Adverse Event Reports

- 13.5.1 Events that do not meet the criteria for CTEP-AERS reporting ([Section 13.2](#)) should be reported at the end of each cycle using the forms provided in the data form packet (See [Section 14.1](#)).
- 13.5.2 COG will forward reports and supporting documentation to the Study Chair, to the FDA (when COG holds the IND) and to the pharmaceutical company (for industry sponsored trials).
- 13.5.3 Adverse events determined to be reportable must also be reported according to the local policy and procedures to the Institutional Review Board responsible for oversight of the patient.

#### 13.6 Reporting Secondary AML/MDS

All cases of acute myeloid leukemia (AML) and myelodysplastic syndrome (MDS) that occur in patients following their chemotherapy for cancer must be reported to the Investigational Drug Branch (IDB) of the NCI Cancer Therapy Evaluation Program

THIS PROTOCOL IS FOR RESEARCH PURPOSES ONLY, SEE PAGE 1 FOR USAGE POLICY

(CTEP) via CTEP-AERS and included as part of the second malignant neoplasm reporting requirements for this protocol (see data submission packet). Submit the completed CTEP-AERS report within 14 days of an AML/MDS diagnosis occurring after treatment for cancer on trials.

### Secondary Malignancy:

A *secondary malignancy* is a cancer caused by treatment for a previous malignancy (e.g., treatment with investigational agent/intervention, radiation or chemotherapy). A secondary malignancy is not considered a metastasis of the initial neoplasm.

All secondary malignancies that occur following protocol treatment be reported via CTEP-AERS. Three options are available to describe the event:

- 1) Leukemia secondary to oncology chemotherapy (e.g., acute myelocytic leukemia [AML])
- 2) Myelodysplastic syndrome (MDS)
- 3) Treatment-related secondary malignancy.

Any malignancy possibly related to cancer treatment (including AML/MDS) should also be reported via the routine reporting mechanisms outlined in each protocol.

### Second Malignancy:

A *second malignancy* is one unrelated to the treatment of a prior malignancy (and is **NOT** a metastasis from the initial malignancy). Second malignancies require **ONLY** routine reporting via CDUS unless otherwise specified.

## 13.7 Reporting Pregnancy, Fetal Death, and Death Neonatal

When submitting CTEP-AERS reports for “Pregnancy”, “Pregnancy loss”, or “Neonatal loss”, the Pregnancy Information Form should be completed and emailed along with any additional medical information to the ADVL1414 COG Study Assigned Research Coordinator. The potential risk of exposure of the fetus to the investigational agent should be documented in the “Description of Event” section of the CTEP-AERS report, along with the source of exposure (mother, father, breastfeeding).

### 13.7.1 Pregnancy

- Patients who become pregnant on study risk intrauterine exposure of the fetus to agents which may be teratogenic. For this reason, pregnancy occurring on study or within 6 months following the last dose of study therapy should be reported in an expedited manner via CTEP-AERS as **Grade 3 “Pregnancy, puerperium and perinatal conditions - Other (Pregnancy)”** under the “Pregnancy, puerperium and perinatal conditions” SOC.
- Pregnancy should be followed until the outcome is known. If the baby is born with a birth defect or anomaly, then a second CTEP-AERS report is required.

### 13.7.2 Pregnancy Loss (Fetal Death)

- Pregnancy loss is defined in CTCAE as “Death in utero.”
- Any pregnancy loss should be reported expeditiously as **Grade 4**

THIS PROTOCOL IS FOR RESEARCH PURPOSES ONLY, SEE PAGE 1 FOR USAGE POLICY

**“Pregnancy loss”** under the **“Pregnancy, puerperium and perinatal conditions”** SOC. Do NOT report a pregnancy loss as a Grade 5 event since CTEP-AERS recognizes any Grade 5 event as a patient death.

### 13.7.3 Death Neonatal

- Neonatal death, defined in CTCAE as **“Newborn deaths occurring during the first 28 days after birth”** that is felt by the investigator to be at least possibly due to the investigational agent/intervention, should be reported expeditiously.
- A neonatal death should be reported expeditiously as Grade 4 “Death neonatal” under the General disorders and administration SOC **when the death is the result of a patient pregnancy or pregnancy in partners of men on study.**
- Do NOT report a neonatal death resulting from a patient pregnancy or pregnancy in partners of men as a Grade 5 event as CTEP-AERS recognizes any Grade 5 event as a patient death.

Pregnancy should be followed up until the outcome of the pregnancy is known at intervals deemed appropriate by her physicians. The “Pregnancy Information Form” should be used for all necessary follow-ups. This form is available at [http://ctep.cancer.gov/protocolDevelopment/electronic\\_applications/docs/PregnancyReportForm.pdf](http://ctep.cancer.gov/protocolDevelopment/electronic_applications/docs/PregnancyReportForm.pdf).

### 13.7.4 Abuse, Misuse or Medication Error

Abuse is the persistent or sporadic, intentional excessive use of the study treatment which is accompanied by harmful physical or psychological effects. A medication error is any preventable incident that may cause or lead to inappropriate study treatment use or patient harm while the study treatment is in the control of the health care professionals or patients. Such incident may be due to health care professional practice, product labeling, packaging and preparation, procedures for administration, and systems, including the following: prescribing, order communication, nomenclature, compounding, dispensing, distribution, administration, education, monitoring, and use. All occurrences of abuse, misuse, or medication error with any study treatment are to be recorded on an SAE report form and sent to Karyopharm Pharmacovigilance, regardless of whether or not an AE or SAE has occurred due to the abuse, misuse, or medication error. If the abuse, misuse, or medication error is associated with an SAE, the SAE report form must be submitted to Karyopharm Pharmacovigilance within 24 hours of awareness. If there is no AE or SAE, the report must be submitted within 24 hours of awareness.

## 14.0 RECORDS, REPORTING, AND DATA AND SAFETY MONITORING PLAN

### 14.1 Categories of Research Records

Research records for this study can be divided into three categories

1. Non-computerized Information: Roadmaps, Pathology Reports, Surgical Reports. These forms are uploaded into RAVE.

THIS PROTOCOL IS FOR RESEARCH PURPOSES ONLY, SEE PAGE 1 FOR USAGE POLICY

2. Reference Labs, Biopathology Reviews, and Imaging Center data: These data accompany submissions to these centers, which forward their data electronically to the COG Statistics & Data Center.
3. Computerized Information Electronically Submitted: All other data will be entered in RAVE with the aid of schedules and worksheets (essentially paper copies of the OPEN and RAVE screens) provided in the case report form (CRF) packet.

See separate CRF Packet, which includes submission schedule.

#### 14.2 Access to Rave for Data Submission/ Data Reporting

Medidata Rave is a clinical data management system being used for data collection for this trial/study. Access to the trial in Rave is controlled through the CTEP-IAM system and role assignments.

Requirements to access Rave via iMedidata:

- A valid CTEP-IAM account; and
- Assigned a Rave role on the LPO or PO roster at the enrolling site of: Rave CRA, Rave Read Only, Rave CRA (LabAdmin), Rave SLA, or Rave Investigator.

Rave role requirements:

- Rave CRA or Rave CRA (Lab Admin) role must have a minimum of an Associate Plus (AP) registration type;
- Rave Investigator role must be registered as an Non-Physician Investigator (NPIVR) or Investigator (IVR); and
- Rave Read Only role must have at a minimum an Associates (A) registration type.

Refer to <https://ctep.cancer.gov/investigatorResources/default.htm> for registration types and documentation required.

Upon initial site registration approval for the study in Regulatory Support System (RSS), all persons with Rave roles assigned on the appropriate roster will be sent a study invitation e-mail from iMedidata. To accept the invitation, site staff must log in to the Select Login (<https://login.imedidata.com/selectlogin>) using their CTEP-IAM username and password and click on the *accept* link in the upper right-corner of the iMedidata page. Site staff will not be able to access the study in Rave until all required Medidata and study specific trainings are completed. Trainings will be in the form of electronic learnings (eLearnings) and can be accessed by clicking on the link in the upper right pane of the iMedidata screen. If an eLearning is required and has not yet been taken, the link to the eLearning will appear under the study name in iMedidata instead of the *Rave EDC* link; once the successful completion of the eLearning has been recorded, access to the study in Rave will be granted, and a *Rave EDC* link will display under the study name.

Site staff that have not previously activated their iMedidata/Rave account at the time of initial site registration approval for the study in RSS will receive a separate invitation from iMedidata to activate their account. Account activation instructions are located on the CTSU website in the Data Management section under the Rave resource materials (Medidata Account Activation and Study Invitation Acceptance). Additional information on iMedidata/Rave is available on the CTSU members' website in the Data Management > Rave section at [www.ctsu.org/RAVE/](http://www.ctsu.org/RAVE/) or by contacting the CTSU Help Desk at [name]

5923 or by e-mail at [[contact]](mailto:[contact]).

### 14.3 CDUS

This study will be monitored by the Clinical Data Update System (CDUS) version 3.0. Cumulative CDUS data will be submitted quarterly to CTEP by electronic means. Reports are due January 31, April 30, July 31 and October 31. This is not a responsibility of institutions participating in this trial.

### 14.4 Data and Safety Monitoring Plan

Data and safety is ensured by several integrated components including the COG Data and Safety Monitoring Committee.

#### 14.4.1 Data and Safety Monitoring Committee

This study will be monitored in accordance with the Children's Oncology Group policy for data and safety monitoring of Phase 1 and 2 studies. In brief, the role of the COG Data and Safety Monitoring Committee is to protect the interests of patients and the scientific integrity for all Phase 1 and 2 studies. The DSMC consists of a chair; a statistician external to COG; one external member; one consumer representative; the lead statistician of the PEP-CTN scientific committee; and a member from the NCI. The DSMC meets at least every 6 months to review current study results, as well as data available to the DSMC from other related studies. Approximately 6 weeks before each meeting of the Phase 1 and 2 DSMC, study chair will be responsible for working with the study statistician to prepare study reports for review by the DSMC. The DSMC will provide recommendations to the COG PEP-CTN Chair and the Group Chair for each study reviewed to change the study or to continue the study unchanged. Data and Safety Committee reports for institutional review boards can be prepared using the public data monitoring report as posted on the COG Web site.

#### 14.4.2 Monitoring by the Study Chair and Developmental Therapeutics Leadership

The study chair will monitor the study regularly and enter evaluations of patients' eligibility, evaluability, and dose limiting toxicities into the study database. In addition, study data and the study chair's evaluations will be reviewed by the COG PEP-CTN Chair, Vice Chair and Statistician on a weekly conference call.

**APPENDIX I: PERFORMANCE STATUS SCALES/SCORES**

Karnofsky		Lansky	
Score	Description	Score	Description
100	Normal, no complaints, no evidence of disease	100	Fully active, normal.
90	Able to carry on normal activity, minor signs or symptoms of disease.	90	Minor restrictions in physically strenuous activity.
80	Normal activity with effort; some signs or symptoms of disease.	80	Active, but tires more quickly
70	Cares for self, unable to carry on normal activity or do active work.	70	Both greater restriction of and less time spent in play activity.
60	Required occasional assistance, but is able to care for most of his/her needs.	60	Up and around, but minimal active play; keeps busy with quieter activities.
50	Requires considerable assistance and frequent medical care.	50	Gets dressed, but lies around much of the day; no active play, able to participate in all quiet play and activities.
40	Disabled, requires special care and assistance.	40	Mostly in bed; participates in quiet activities.
30	Severely disabled, hospitalization indicated. Death not imminent.	30	In bed; needs assistance even for quiet play.
20	Very sick, hospitalization indicated. Death not imminent.	20	Often sleeping; play entirely limited to very passive activities.
10	Moribund, fatal processes progressing rapidly.	10	No play; does not get out of bed.

**APPENDIX II: CORRELATIVE STUDIES GUIDE**

Correlative Study	Appx.	Tube Type	Blood Volume per Sample	Cycle 1 Volume
Pharmacokinetics (Parts A and B)	III	Lavender Top	1 mL	9 mL
Pharmacokinetics (Part C)	III	Lavender Top	1 mL	10 mL
PD- Plasma Proteins	IV-A	Lavender Top	2 mL	4 mL
PD- Whole Blood	IV-B	PAXgene tube	2.5 mL	10 mL
Total Blood Volume –Cycle 1 (Parts A and B)				23 mL
Total Blood Volume –Cycle 1 (Parts C)				24 mL
Tumor Tissue (Part C)	V			

**APPENDIX III: PHARMACOKINETIC STUDY FORM**

COG Pt ID # \_\_\_\_\_ ACC # \_\_\_\_\_

Please do not write patient names on this form or on samples.

Cycle 1, Day 1 Date: \_\_\_/\_\_\_/\_\_\_/\_\_\_/\_\_\_ Dose Level: \_\_\_\_\_mg/m^2 Dose Administered: \_\_\_\_\_mg

Plasma samples (1 mL) will be collected for pharmacokinetic studies at the time points listed in the table below. Record the exact date and time each sample is drawn and the time of the selinexor administration. In the event the dose is vomited within 30 minutes after administration on Cycle 1, Day 1 **and** there is no visible evidence of the tablet, the PK samples #2-9 should be collected after the second dose on Cycle 1, Day 3.

Blood Sample No.	Barcode # (from Sample Label)	Time Point	Scheduled Sample Collection Time	Scheduled Selinexor Time Point	Actual Date Sample Collected or Dose Given	Actual Time Sample Collected or Dose Given (24-hr clock)
1		Cycle 1, Day 1	Prior to Dose on Cycle 1, Day 1		___/___/___	__:__:__
				Cycle 1, Day 1	___/___/___	__:__:__
2		Cycle 1, Day 1	30 min. after Day 1 dose		___/___/___	__:__:__
3		Cycle 1, Day 1	1 hour after Day 1 dose		___/___/___	__:__:__
4		Cycle 1, Day 1	2 hour after Day 1 dose		___/___/___	__:__:__
5		Cycle 1, Day 1	3 hour after Day 1 dose		___/___/___	__:__:__
6		Cycle 1, Day 1	4 hour after Day 1 dose		___/___/___	__:__:__
7		Cycle 1, Day 1	6 hour after Day 1 dose		___/___/___	__:__:__
8		Cycle 1, Day 1	8 hour after Day 1 dose		___/___/___	__:__:__
9		Cycle 1, Day 2	24 (± 2) hr after Day 1 dose		___/___/___	__:__:__

Part C: An additional PK sample will be collected after 2 doses prior to Tumor Resection. Surgical resection should occur after dose on Day 8 but before dose on Day 15 of Cycle 1.

Blood Sample No.	Barcode # (from Sample Label)	Time Point	Scheduled Sample Collection Time	Scheduled Tumor Resection Date	Actual Date Sample Collected or Date of Resection	Actual Time Sample Collected or Dose Given (24-hr clock)
10		After 2 doses	Prior to Tumor Resection		___/___/___	__:__:__
				___/___/___	___/___/___	__:__:__

Refer to [Section 8.3](#) processing and shipping details. One copy of this Pharmacokinetic Study Form should be uploaded into RAVE.

If this form will be used as a source document, the site personnel who collected the samples must sign and date this form below:

Signature: \_\_\_\_\_

Date: \_\_\_\_\_

THIS PROTOCOL IS FOR RESEARCH PURPOSES ONLY, SEE PAGE 1 FOR USAGE POLICY

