**Amendment #4:**

Week	Day	Agent: Selinexor
1	1	X
2	8	X
3	15	X
4	22	X

With Amendment #4, patients will receive selinexor once weekly, on Days 1, 8, 15, and 22 of a 28-day cycle. The drug will be administered in tablet form with food. Patients may continue for a maximum of 24 cycles. Refer to [Section 7.3](#) for recommended supportive care guidelines.

Drug doses should be adjusted based on the BSA calculated from height and weight measured within 7 days prior to the beginning of each cycle (See [Appendix VI](#)). If a dose is vomited within 30 minutes of administration and there is visible evidence of the tablet, the dose should be repeated. If the tablet is not visible, or the dose is vomited later than 30 minutes after administration, the dose should not be repeated. The patient/caregiver should make a note of the vomited dose and whether there is visible evidence of the tablet on the pill diary and proceed with the next dose at the next scheduled time of administration.

Selinexor is supplied by Karyopharm Therapeutics. **Do not use commercial supply.**

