### 11.5 Pharmacokinetic and Correlative Studies and Response Analysis

A descriptive analysis of pharmacokinetic (PK) parameters of selinexor will be performed to define systemic exposure, drug clearance, and other pharmacokinetic parameters. The PK parameters will be summarized with simple summary statistics, including means, medians, ranges, and standard deviations (if numbers and distribution permit).

While the primary aim of this study is to evaluate the toxicity of selinexor, patients will have disease evaluations performed as indicated in [Section 8.1](#). Disease response will be assessed according to RECIST criteria for patients with solid tumors, or the criteria specified in [Section 12.6](#) for patients with CNS tumors, and will be reported descriptively.

Clinical benefit for Part B will be defined in one of two ways, either PR or CR on two consecutive 2D measurements on standard imaging (see [Section 12.6](#)) or as > 12 weeks from first dose without progressive disease, while clinical benefit in Part C will be defined as no visible disease progression six months from the start of treatment. Clinical benefit rate will be summarized separately for each of Parts B and C with 95% confidence intervals.

All these analyses will be descriptive and exploratory and hypotheses generating in nature.

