**APPENDIX IV-A: PHARMACODYNAMICS STUDY FORM- PLASMA PROTEINS**

COG Pt ID # \_\_\_\_\_ ACC # \_\_\_\_\_

Please do not write patient names on this form or on samples.

Cycle 1, Day 1 Date: \_\_\_/\_\_\_/\_\_\_/\_\_\_/\_\_\_ Dose Level: \_\_\_\_\_ mg/m^2 Dose Administered: \_\_\_\_\_ mg

Plasma samples (2 mL) will be collected for Plasma Protein studies on cycle 1, day 1, pre- and 4 hours after dose is given in consenting patients. Record the exact date and time each sample is drawn and the time of the selinexor administration.

Blood Sample No.	Time Point	Scheduled Sample Collection Time	Scheduled Selinexor Time Point	Actual Date Sample Collected or Dose Given	Actual Time Sample Collected or Dose Given (24-hr clock)
1	Cycle 1, Day 1	Prior to Dose on Cycle 1, Day 1		___/___/___	__:__:__
			Cycle 1, Day 1	___/___/___	__:__:__
2	Cycle 1, Day 1	4 hr after Day 1 dose		___/___/___	__:__:__

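### The PK form re-times sampling only for a Day 1 dose vomited within 30 minutes with no tablet seen, and the PD forms have no vomiting rule, so partly lost doses have no defined handling

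*Combined protocol and SAP*

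**What the plan says.** Appendix III sets two joint conditions for re-timing the PK profile. The first is the time window: "In the event the dose is vomited within 30 minutes after administration on Cycle 1, Day 1". The second follows in the same sentence: "there is no visible evidence of the tablet, the PK samples #2-9 should be collected after the second dose on Cycle 1, Day 3". The form has a single line for the Cycle 1 Day 1 dose and labels samples 2 to 9 relative to that dose. It has no field for emesis.

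Section 5.1 (Amendment #4) gives the dosing rules: "If a dose is vomited within 30 minutes of administration and there is visible evidence of the tablet, the dose should be repeated" and "If the tablet is not visible, or the dose is vomited later than 30 minutes after administration, the dose should not be repeated". It asks for the vomited dose, and whether a tablet was seen, to be noted in the pill diary. The same section sets the current schedule: "With Amendment #4, patients will receive selinexor once weekly, on Days 1, 8, 15, and 22 of a 28-day cycle".

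On analysis, Section 11.5 says "The PK parameters will be summarized with simple summary statistics, including means, medians, ranges, and standard deviations", if numbers and distribution permit. Neither 8.3 nor 11.5 defines a PK-evaluable profile.

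On PD, Appendix IV-A takes plasma protein samples on Cycle 1 Day 1, "pre- and 4 hours after dose is given in consenting patients". Appendix IV-B and Section 8.4 use the same two time points. None of the three mentions vomiting.

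**The concern.** Thirty minutes may suit a re-dosing decision, but it is a weak limit for the validity of a PK profile when the trial's own median time to peak is 2 to 4 h. A dose vomited at 45 minutes or 1 h can lose a real part of its content. AUC and Cmax then come out low, and apparent clearance (nominal dose over AUC) comes out high. The error has one direction, the groups are small (about six per dose level), and PK is primary aim 1.1.3. Section 2.8 also relies on comparing pediatric with adult exposure.

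The PD gap is different in kind. When a dose is vomited within 30 minutes and no tablet is seen, Appendix III itself abandons that dose for PK. The 4 h PD sample still belongs to it, so PK and PD for that patient would describe different doses (secondary aim 1.2.2).

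**Working it through.** **Step 1. Set the rules side by side.**

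| Event after the Day 1 dose | Dosing (5.1) | PK (Appendix III) | PD (8.4, Appendices IV-A, IV-B) |
|---|---|---|---|
| Vomited within 30 min, no tablet seen | Not repeated | Samples 2–9 move to a Day 3 dose | No instruction; 4 h sample stays on Day 1 |
| Vomited within 30 min, tablet seen | Repeated | No instruction; one dose-time line | No instruction |
| Vomited after 30 min | Not repeated | No instruction; Day 1 sampling goes on | No instruction |

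Only the first row has a PK rule, and it points to Day 3. The Amendment #4 dosing days are 1, 8, 15 and 22, so that rule cannot be carried out as written.

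**Step 2. Size the effect.** The plan has no figure of its own to reproduce. Inputs from Table A: median Tmax 2 h and mean half-life 7.9 h at 35 mg/m² (n = 19); 4 h and 7.2 h at 20 mg/m² (n = 12). Assumptions: one compartment, first-order absorption without lag, all unabsorbed drug lost on vomiting, and an affected patient whose true CL/F equals the group mean.

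- ke = ln 2 / t½ = 0.0877/h and 0.0963/h.
- Solve ln(ka/ke)/(ka − ke) = Tmax: ka = 1.511/h and 0.516/h.
- Fraction absorbed by time t: F(t) = 1 − exp(−ka·t).
- CL/F computed on the nominal dose is inflated by 1/F(t).
- One such profile in six raises mean CL/F by (1/F − 1)/6.

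| Vomiting at | Tmax 2 h: F, 1/F, rise in mean of six | Tmax 4 h: F, 1/F, rise in mean of six |
|---|---|---|
| 0.5 h | 53%, 1.89, 14.8% | 23%, 4.40, 56.6% |
| 1 h | 78%, 1.28, 4.7% | 40%, 2.48, 24.7% |
| 2 h | 95%, 1.05, 0.9% | 64%, 1.55, 9.2% |
| 4 h | 99.8%, 1.00, under 0.1% | 87%, 1.15, 2.4% |

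(Computed from unrounded values.)

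**Step 3. Average over the window.** If the vomiting time is uniform from 0.5 to 4 h, mean inflation is [ln(exp(4ka) − 1) − ln(exp(0.5ka) − 1)] / (3.5ka). This gives 1.120 (Tmax 2 h) and 1.745 (Tmax 4 h). One profile in six then raises mean CL/F by (1.120 − 1)/6 = 2.0% and (1.745 − 1)/6 = 12.4%.

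For AUC, mean F over the window is 1 − [exp(−0.5ka) − exp(−4ka)]/(3.5ka) = 0.912 and 0.643. Mean AUC falls by (1 − 0.912)/6 = 1.5% and (1 − 0.643)/6 = 6.0%.

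**Step 4. Spread between patients.** Step 2 uses median Tmax. Across the 35 mg/m² Tmax range of 0.5 to 6 h, the same model puts the fraction absorbed by 30 minutes anywhere from 99% to 13%. A single patient can therefore fall well outside these averages in either direction.

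**The case against.** The other side has substantial points.

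- **Retention is not stated.** Section 11.5 does not say that compromised profiles are kept. It is silent, and it lists medians and ranges as well as means. A reader might infer that the plan commits to analysing partly vomited doses as full doses. The text does not support that; it shows only that nothing prevents it. This objection stands.
- **Vomited doses can be traced.** Section 5.1 requires a diary note, and Section 8.1 (footnote 4) has the diary reviewed and uploaded weekly in Cycle 1. This stands in part: the diary has no dedicated field for the clock time of emesis, which is what decides how much was absorbed.
- **Early emesis is probably uncommon.** Section 7.3.2.1 describes acute emesis as infrequent, and prophylaxis is strongly recommended in Cycles 1 and 2. This stands. Any specific rate would be a guess.
- **Dose decisions do not use the PK summary.** The Amendment #4 levels are fixed in 5.3.1 and escalation in 11.3 follows DLT counts. This stands.
- **A repeated dose does little harm.** Section 8.3.3 asks for the exact administration time, and if the repeat is prompt only the first one or two samples precede it. This largely stands; what is missing is a place to record the second time and a statement of which dose is time zero.
- **The 4 h PK sample shows what the PD sample saw.** This is true when both stay on Day 1. It fails when PK samples 2 to 9 move and PD does not.

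**Conclusion.** The gap is real and modest. For two of the three vomiting cases the plan gives no PK instruction, for the third it names a dosing day that the current schedule lacks, and for PD it gives no instruction in any case. By default, sampling after later emesis continues against the nominal dose, and whether that profile enters the summary is left to be decided after the data are seen.

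The expected effect on mean CL/F is about 2% to 12% for one affected profile in six, under the stated model and a uniform vomiting time between 0.5 and 4 h. The upper figure comes from the 20 mg/m² data, a dose outside the Amendment #4 levels of 35, 45 and 55 mg/m². No Tmax is given for 45 or 55 mg/m². Complete loss of unabsorbed drug is a worst case.

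A reader might infer a routine rise of 15% to 25%. That needs vomiting at 0.5 h with Tmax 2 h (14.8%) or at 1 h with Tmax 4 h (24.7%); at these median Tmax values, effects of that size arise only close to 30 to 60 minutes. A reader might also infer that dose selection is distorted, but no escalation rule uses the PK summary and Section 11.5 calls these analyses descriptive and exploratory. How often the problem would arise cannot be stated, because the documents give no rate of early vomiting.

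**What to change.** 1. On Appendices III, IV-A and IV-B, add fields for the clock time of any emesis after the sampled dose, whether a tablet was seen, and the time of any repeat dose.
2. In Section 11.5, flag profiles with emesis during the absorption phase or with a repeated dose. Tie the cut-off to observed Tmax and fix it before the PK analysis. Report AUC, Cmax and CL/F with and without the flagged profiles.
3. Whenever PK samples move to another dose, move the 4 h PD sample to that same dose. The existing trigger is known by 30 minutes, before the 4 h sample is drawn, so this adds no blood.
4. Reconcile the Day 3 reference in Appendix III with the current dosing days in Section 5.1.

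Repeat sampling after late emesis should not be required. Day 1 samples would already have been drawn, and repeating samples 2 to 9 at 1 mL each would add up to 8 mL to the 23 to 24 mL Cycle 1 total in Appendix II. The re-dosing rule is a clinical matter and stays unchanged.

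The cost is a few form fields, one or two sentences in 11.5, and slightly fewer profiles in the summary that leaves out flagged ones. No patients are added.
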